Study Title: Improving Influenza Vaccination Delivery Across a Health System by the Electronic Health Records Patient Portal RCT 5 (LADHS)

Initial IRB Approval: 12/20/2017

RCT 5 (LADHS) IRB Approval: 8/29/2022

Clinical Trials Registration: NCT05535777

Significance:

Previous studies have shown that low-cost, behavioral nudges through texting can increase influenza vaccination uptake compared to usual care. However, there are limited studies that evaluate the effect of decreasing friction/barriers to scheduling especially within safety net populations. This study will examine the effect of strategies to reduce friction/barriers to scheduling including bidirectional text messages, texts for patients to call for direct scheduling without wait time, and texts highlighting MediCal health plan transportation resources on influenza vaccination rates in adults within the 2022-2023 flu season.

Objectives:

This will be a randomized clinical trial (RCT) to test the impact of text message innovations on receipt of influenza vaccination during the 2022-23 season. Specifically, we will simultaneously test, using a comparative effectiveness trial design, the effect of the following 3 interventions, all compared to standard text messages:

- Enhanced texting (with a callback by a trained call-center staff member to schedule a vaccine visit if the patient presses "1" in response to the text
- Enhanced Bidirectional texting- with a texting response from a trained call-center staff member who will help the patient schedule a vaccine visit through a series of back-andforth texts
- Provision of transportation information- with information within the text messages that highlight to patients that MediCal will pay for transportation to a vaccine visit

Study Design:

The study design is shown in this figure. Intervention arms are described below.

We will send the total patient population of around 250,000 one of several types of text message reminders.

Selection of Patients:

Patient eligibility: Any patient who is deemed by LADHS to be an LADHS patient will become the patient denominator. Primary care patients who are empaneled to a primary care provider within DHS are assigned as follows: (1) assigned through managed care plans, (2) self-pay but linked with a provider, or (3) uninsured but assigned. We will include all patients over 6 months of age.

Identification of families (i.e., households): We will group families using one of two possible methods. First, LADHS has an identifier that ties family members together. It is called the "Family Budget Unit." We will explore this method. If it does not work, we will use another method that we have utilized successfully in the UCLA-based study from which this study is derived. We will assume that people living in the same address belong to the same family. As a secondary measure, we use a telephone number as a linking number (i.e., if two people have the same telephone number, we assume they are from the same household).

We will randomly allocate families to one of the study arms shown above and send family members the allocated text message. All family members will therefore receive the same text message. This is meant to reduce confusion among patients. For the analysis, we will randomly select one index patient per household for analysis. This follows Cochrane criteria for being included in meta-analyses. We will attempt to affiliate index patients with practices, and randomize patients (families) within these practices.

Assignment to the intervention: All patients will be eligible for the intervention. There are no specific inclusion or exclusion criteria. Since we will send up to 3 text messages in October-December 2022, we will search the EHR for whether or not the patient received an influenza vaccination this season. If yes, the patients will be dropped form the denominator of patients needing a text message reminder. We will search the EHR prior to each of the text message rounds.

Review of medical records is needed in order to obtain the information about (a) influenza vaccination dates this upcoming season, and (b) address (in order to group patients into households as described above. We will review the EHR prior to each round of text messages to see if patients had received an influenza this season.

Description of the Interventions:

Text messages will begin to be sent in early October. We will randomly spread out the calls throughout the day and week in order to minimize unnecessary overload for the call center when patients text back a "1" response that they would like a call or text message to help them. We can do this by randomizing patients into batches so that there is no systematic time-of-day or day-of-week for any patients. We will send up to 3 reminders this upcoming season.

Standard Texts (n=232,950): Patient randomized to this study arm will receive up to 3 text messages, reminding them about the importance of influenza vaccination. The messages themselves are shown below. The standard texts will include a clinic call back number and patient portal self-scheduling for patients to schedule their influenza vaccines. The direct scheduling texts includes a direct number to an agent that can help schedule and answer questions on the phone in real time. The texts with a direct number to schedule will link a specified phone number to call and schedule. This number would be answered by a central agent quickly and a patient could schedule their flu shot at any clinic site. This specific phone number would not go through the multiple option menus a patient would normally experience when calling their clinic.

Standard Texts with Transportation (n=3,050): The standard texts with transportation includes phone number for patients to reserve transportation to a vaccination appointment based on MediCal health plan transportation resources.

Enhanced Texts- Callback by a person (n=7,000): Patient randomized to this study arm will receive a phone call back by a call center agent if they press "1" in response to a question on the original text message. The call center agent's job is to schedule patients for clinical visits. These call center agents will be trained by our faculty and staff and will have the usual HIPAA and other patient confidentiality training.

Enhanced Bidirectional Texts- to help schedule a vaccine visit (n=7,000): Patients randomized to this study arm will receive a text message from a call center agent if they press "1" in response to a question on the original text message. The bidirectional texts will have an agent who can answer questions and schedule an appointment through text message back-and-forth conversations with the patient. Bidirectional texts will be exchanged on a HIPAA compliant bidirectional text messaging platform. The patient will use the regular SMS function on their cellphone and the agent will receive and respond to the bidirectional text on the HIPAA compliant platform.

Text Message Wording:

The wording of each of the text messages is shown in the figure below. We will have these translated into Spanish. LADHS patients have the option of receiving text messages in English or Spanish.

Prepped Text Messages for DHS Flu Campaign 2022 - 2023

Standard Text:

#PCMH#: #FirstName#, your flu shot is ready! Call your clinic at #ExternalRefNo# or visit the LA Health Portal at http://bit.ly/BookFluShot if you want this shot held for you.

Standard Texts (+ Transportation)

#PCMH#: #FirstName#, your flu shot is ready! Call your clinic at #ExternalRefNo# or visit the LA Health Portal at http://bit.ly/BookFluShot if you want this shot held for you. You can call #Health Plan Phone Number# to schedule a free ride your flu shot through #Health Plan Name#

Examples (Transportation)

• Standard Texts (+ Transportation) - LA Care

#PCMH#: #FirstName#, your flu shot is ready! Call your clinic at #ExternalRefNo# or visit the LA Health Portal at http://bit.ly/BookFluShot if you want this shot held for you. You can call [contact] to schedule a free ride for your flu shot through your LA Care health plan.

• Standard Texts (+ Transportation) - Health Net

#PCMH#: #FirstName#, your flu shot is ready! Call your clinic at #ExternalRefNo# or visit the LA Health Portal at http://bit.ly/BookFluShot if you want this shot held for you can call [contact] to schedule a free ride for your flu shot through your Health Net health plan.

Enhanced Prompt for Phone Scheduling:

#PCMH#: #FirstName#, your flu is ready! Call our direct number xxx-xxx to connect with an agent to hold this flu shot and schedule an appointment now.

Bidirectional Texts:

#PCMH#: #FirstName#, your flu shot is ready! Reply Y if you want this shot held for you and an agent will text you back to schedule an appointment.

For more details, please see:

https://docs.google.com/document/d/12ERynaBMjzpIpjcPJDoBCu-8GA7cVBbYV8zko3mCBnM/edit

And a brief here:

https://docs.google.com/document/d/1Au5l7zjVqJSpQzi5NF7YvLR07mmyaMlz89dpDHWOob8/ edit

Data Management:

All study data, including CAIR2 data and DHS EMR and administrative data will be prepared by the DHS-CTSI Informatics Core in accordance with the DHS Research Oversight Board policy. [name] will submit all data requests to the DHS helpdesk, which includes verification of procedural compliance with IRB and ROB approval screening for DHS-based research. Only HIPAA-limited or deidentified data sets will be transferred for analysis purposes; compliance with the DHS secure data transfer process to UCLA and/or USC will be managed by [name] as DHS Principal Investigator. Any links between identified data and deidentified data will be stored only on DHS premises. Patient contact lists and personalized data elements will be exclusively maintained on premises by the Informatics Core, responsible for implementing the patient assignment and personalization templates.

Statistical Analysis of Randomized Trial. We will perform separate evaluations of the impact of the text enhancements (callback and bidirectional texting) on the one hand, and transportation messaging on the other hand. For both analyses, we will use multivariable log-binomial regression models with vaccination status at the end of the campaign as the outcome variable. Regressions will include indicators for each intervention as fixed effects, with the standard text condition as the reference group, and potentially clinic random effects, depending on retrospective analysis results. Models will also adjust for patient age, gender, race/ethnicity, insurance, and whether the patient was vaccinated in at least one of the prior two flu seasons. Secondary analysis will include subgroup interactions with intervention indicators to assess heterogeneity of treatment effects. In exploratory analyses, we will investigate interactions between interventions, questions related to modality of message delivery, as well as whether encounter type, click rates on messages, and distance to the health care facility from the home address affect influenza vaccination rates.

In addition, we will evaluate the loss to follow-through rates (scheduling an appointment, but did not complete the appointment) by patient demographics, as distance to the health care facility from the home address).

For the evaluation of text enhancements, we will perform a 3-fold Bonferroni correction accounting for pairwise comparison of intervention arms, using a two-sided significance level of 0.017. For the evaluation of transportation messaging, we will use a two-sided significance level of 0.05. All analyses will be intention-to-treat, and will be performed using SAS v. 9.4 (SAS Institute Inc., Cary, NC).

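### If families are grouped by Family Budget Unit, the plan as most naturally read does not link them by phone number, so one handset can be assigned texts from two arms

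*Combined protocol and SAP*

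**What the plan says.** The paragraph on identification of families opens with "We will group families using one of two possible methods". The first method is the Family Budget Unit held by the health system. Of it the plan says "We will explore this method. If it does not work, we will use another method that we have utilized successfully". The second method treats people at the same address as one family. Directly after that address rule comes "As a secondary measure, we use a telephone number as a linking number", with the explanation that two people with the same number are taken to be one household.

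The family is then the unit of randomisation: "We will randomly allocate families to one of the study arms shown above and send family members the allocated text message". The stated reason is "All family members will therefore receive the same text message. This is meant to reduce confusion among patients". For the analysis, "For the analysis, we will randomly select one index patient per household for analysis".

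The paragraph on assignment to the intervention lists what must be taken from the medical record. For grouping it names address and does not name telephone number. Nothing elsewhere in the document removes duplicate numbers, checks how many arms a handset is assigned to, or plans a sensitivity analysis for shared phones.

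**The concern.** Every arm is delivered to a phone, but the preferred grouping rule is administrative. The study includes patients from the age of 6 months, so messages about young children have to reach a caregiver's phone, and relatives may handle messages for one another. Where such people belong to different Family Budget Units, their arms are drawn independently.

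Two things are then at stake. First, one handset may carry the standard text for one patient and the phone-scheduling, bidirectional or transportation text for another. Whoever holds the phone can act on either, so the scheduling routes under comparison are mixed. Second, each unit supplies its own index patient, so two people whom the fallback rule would place in one household enter the analysis as if from separate households. The planned model has at most a clinic random effect and no household term to absorb this.

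**Working it through.** **Inputs** (Description of the Interventions): standard 232,950; transportation 3,050; enhanced callback 7,000; enhanced bidirectional 7,000. Their sum is 232,950 + 3,050 + 7,000 + 7,000 = 250,000, which reproduces the population of around 250,000 given under Study Design. The arm shares are 93.18%, 1.22%, 2.80% and 2.80%.

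**Assumptions.** Units are allocated independently in these proportions, including within practices, and each shared phone serves exactly one other unit. The results concern assignment. Delivery could be somewhat lower, because patients already vaccinated are dropped before each text round.

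**Step 1: chance that the other unit is in a different arm, given own arm k** = 1 − n_k/N.

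- Standard: 1 − 232,950/250,000 = 6.8%
- Each enhanced arm: 1 − 7,000/250,000 = 97.2%
- Transportation: 1 − 3,050/250,000 = 98.8%

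For an enhanced-arm patient the other unit is in the standard arm with probability 93.18%, and in another intervention arm with probability 97.20% − 93.18% = 4.02%. Over all pairs of units sharing a phone, the chance of different arms is 1 − (0.9318² + 0.0122² + 0.028² + 0.028²) = 13.0%.

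**Step 2: share of each arm affected.** Let s be the proportion of patients whose number also serves another Family Budget Unit. The documents do not give s, so the values below are assumptions. Affected share = s × (1 − n_k/N).

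| s (assumed) | Standard | Each enhanced arm | Transportation |
|---|---|---|---|
| 2% | 0.14% | 1.94% | 1.98% |
| 5% | 0.34% | 4.86% | 4.94% |
| 10% | 0.68% | 9.72% | 9.88% |
| 20% | 1.36% | 19.44% | 19.76% |

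As a proportion of the arm, exposure is about 14 times higher in the small arms (97.2/6.82 = 14.3).

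**Step 3: headcount.** Affected patients per unit of s:

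- Intervention arms: 2 × 7,000 × 0.972 + 3,050 × 0.9878 = 16,621
- Standard arm: 232,950 × 0.0682 = 15,887

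The split is 51% to 49%. At s = 10% it is about 1,662 intervention patients and 1,589 standard patients.

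**Step 4: controls exposed to one particular enhanced arm** = 2.8% × s, which is 0.14%, 0.28% or 0.56% of the standard arm at s = 5%, 10% or 20%.

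**Step 5: after a merge on phone number.** All patients on one handset share an allocation, so the chance of two arms on that handset is 0 in every arm.

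**The case against.** The plan never says that phone numbers are ignored under the Family Budget Unit. The sentence on the secondary measure could be read as supplementing either method. No criterion defines when the first method fails, so a unit that splits shared phones might count as failing. Listing address among the record items suggests that the address route, with its phone step, was a live expectation. The operational documents linked under the message wording might settle the matter but are not part of the text. These points stand as far as they go: the wording is ambiguous rather than an explicit exclusion. But a choice of one method out of two, with the phone step placed directly after the address rule, reads more naturally as phone linkage in the fallback only.

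A reader might go further and infer that the contrast is diluted toward no effect, mainly in the small arms. The documents do not support that.

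- A cross-exposed intervention patient still receives the full intervention text, addressed to them by first name. The second message is nearly always the standard one, addressed to someone else.
- The transportation text already contains the standard wording, so an extra standard text adds no competing route there. An additional reminder could even raise uptake.
- Dilution through controls who see an enhanced text is negligible (Step 4).
- Putting a number on lost effect would need the sharing rate, the true effect and the fraction lost, and the document gives none of them.

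Nor does the plan promise one arm per handset. Its stated aim is to limit confusion by giving members of a family the same message. The relevant sharing rate is also narrower than phone sharing in general, because sharing within a unit is already covered.

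**Conclusion.** The gap is real but conditional. It arises only if the Family Budget Unit is adopted and phone linkage is confined to the fallback, which is the more natural reading. In that case one handset can be assigned two arms, and one household, as the fallback rule would define it, can supply two index patients.

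The arm-specific chances of 97.2%, 98.8% and 6.8% follow from the stated arm sizes, given a phone shared with one other independently allocated unit. The concentration in the small arms is true only as a proportion of each arm, since the headcount is about even. How many patients are affected depends on a sharing rate that is not stated, so materiality cannot be established from the document; it is probably small. The contrast would be blurred, in a direction that is not fixed. This is a cheap improvement to the design, not a demonstrated threat to the result.

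**What to change.** State that, whichever grouping method is used, groups sharing the mobile number to which texts are sent are merged into one randomisation unit before allocation, and that one index patient is drawn per merged unit. Leave out of the merge blank or placeholder numbers, and numbers listed for implausibly many patients, using a cap set before allocation. Without that cap, a number recorded for many unrelated people could chain separate families into one large unit.

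The cost is one linkage step on contact lists that the Informatics Core already maintains, and slightly fewer randomisation units and index patients. It has to be done before allocation, because it cannot be applied once texts have gone out.

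### Analysing one index patient per household is valid, but it gives up precision that the other randomised family members could supply, mainly in the 3,050 and 7,000 arms

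*Combined protocol and SAP*

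**What the plan says.** Under Study Design: "We will send the total patient population of around 250,000 one of several types of text message reminders". Description of the Interventions gives four arm sizes: 232,950 (standard texts), 3,050 (standard with transportation), 7,000 (callback) and 7,000 (bidirectional).

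Under Identification of families: "We will randomly allocate families to one of the study arms shown above and send family members the allocated text message". It continues: "All family members will therefore receive the same text message". On the analysis set: "For the analysis, we will randomly select one index patient per household for analysis". The reason given is conformity with Cochrane criteria for inclusion in meta-analyses.

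Data Management has registry (CAIR2), medical-record and administrative data prepared centrally. The Statistical Analysis section specifies log-binomial models for vaccination status at the end of the campaign. Clinic random effects are a possibility and there is no family term. The enhancement comparisons are tested at 0.017, the transportation comparison at 0.05. The documents give no household count, household size, within-family correlation, or power calculation.

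**The concern.** The non-index members are eligible, randomised and texted, and their outcome should sit in the same central sources as the index patient's. Leaving them out of the effect estimate saves little and costs information.

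The standard arm is so large that precision depends almost wholly on the small arms, so the loss falls where data are scarcest. The enhancement contrasts are also tested at the stricter level, and the secondary subgroup interactions need more information still. A further, smaller cost is that the estimate depends on which family member the random draw happens to pick.

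**Working it through.** **Inputs from the documents.** The arm sizes reproduce the texted total: 232,950 + 3,050 + 7,000 + 7,000 = 250,000. The arm sizes therefore appear to count texted patients, and the analysed number is the number of families.

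**Assumptions (not in the documents).** Families with k = 1, 2, 3, 4 patients occur with shares w = 0.60, 0.25, 0.10, 0.05 in every arm. Within-family correlation r is exchangeable at 0.3 or 0.5. The vaccination rate is 30%, the same for all family sizes.

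**Families per arm.** The mean size is 0.60×1 + 0.25×2 + 0.10×3 + 0.05×4 = 1.6. Index patients number 3,050/1.6 ≈ 1,906, 7,000/1.6 = 4,375 and 232,950/1.6 ≈ 145,594.

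**Effective observations per family.** The index rule gives 1. The alternatives are:

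- *All members, each weighted 1/k.* The average variance of a family mean is Σ w(1+(k−1)r)/k. At r = 0.3: 0.600 + 0.1625 + 0.0533 + 0.0238 = 0.840. At r = 0.5: 0.600 + 0.1875 + 0.0667 + 0.0313 = 0.885. Each term is at most w when r ≤ 1, so this is never less precise than the index rule.
- *Exchangeable working correlation.* Σ wk/(1+(k−1)r). At r = 0.3: 0.600 + 0.385 + 0.188 + 0.105 = 1.277. At r = 0.5: 0.600 + 0.333 + 0.150 + 0.080 = 1.163.
- *Fully patient-weighted (independence weights, robust errors).* (Σ wk)² / Σ wk(1+(k−1)r) = 2.56/(1.6 + 1.7r). At r = 0.3: 2.56/2.11 = 1.213. At r = 0.5: 2.56/2.45 = 1.045. It equals 1 at r = 0.96/1.7 ≈ 0.56 and falls below 1 beyond that.

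The SE ratio to the index rule is 1/√(effective observations):

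| Analysis | Effective obs., r = 0.3 | SE change | Effective obs., r = 0.5 | SE change |
|---|---|---|---|---|
| 1/k weights | 1/0.840 = 1.191 | −8% | 1/0.885 = 1.129 | −6% |
| Exchangeable | 1.277 | −12% | 1.163 | −7% |
| Patient-weighted | 1.213 | −9% | 1.045 | −2% |

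**In percentage points, r = 0.3.** The unadjusted SE of a risk difference is √[0.21(1/n₁ + 1/n₂)] under the index rule, multiplied by the SE ratio for the alternatives:

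| Contrast | Index rule | 1/k weights | Exchangeable |
|---|---|---|---|
| Transportation vs standard | 1.056 | 0.968 | 0.935 |
| Each enhancement vs standard | 0.703 | 0.644 | 0.622 |
| Callback vs bidirectional | 0.980 | 0.898 | 0.867 |

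**Range.** If all families had the same size m, the three weightings would coincide and the information ratio to the index rule would be m/(1+(m−1)r). It runs from 1.25/1.175 = 1.06 (m = 1.25, r = 0.7) to 3/1.2 = 2.5 (m = 3, r = 0.1), an SE reduction of 3% to 37%. More central cases are 1.5/1.25 = 1.2 (m = 1.5, r = 0.5; 9%) and 2/1.3 = 1.54 (m = 2, r = 0.3; 19%).

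**The case against.** The case for leaving the plan alone is substantial. Drawing one patient at random per family is a deliberate, openly stated choice with a reason attached. It removes within-family correlation without a model, keeps every randomised family in the comparison, and neither biases the arm contrast nor inflates type I error. All of that stands.

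Several stronger readings are tempting and are not supported:

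- *The stated arm sizes are wrong or overstate the analysed n.* The documents present them as the number in each texting arm, never as analysed numbers, and no power figure uses them. What is missing is a label.
- *The rule breaches intention-to-treat.* It does not; selection is random and every family is analysed as allocated.
- *The household-weighted estimate is the wrong one because eligibility is by patient.* It is a legitimate target, though unnamed in the plan. Exchangeable weighting would not deliver a patient-weighted answer either: at r = 0.3 a four-patient family counts 4/1.9 ≈ 2.1, not 4.
- *Using everyone always narrows the intervals.* A fully patient-weighted analysis loses precision above r of about 0.56 under the assumed distribution. At r = 0.7 its SE is 4% larger than under the index rule (2.56/2.79 = 0.918).

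The evidence on outcome data also has a limit. The record search before each text round decides who still needs a message and is not the outcome. The documents do not say whether the central extraction covers non-index members, so availability is a reasonable expectation only.

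These points do not remove the efficiency argument for the 1/k and exchangeable options. The meta-analysis reason is met equally well by keeping the index analysis in second place.

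**Conclusion.** The point holds as one of efficiency, not validity. Under the assumed family-size distribution, an all-member analysis lowers the SE by about 6–8% with 1/k weights and 7–12% with an exchangeable working correlation, for r between 0.5 and 0.3. At r = 0.3 and a 30% rate, the exchangeable option saves about 0.12 points of SE on the transportation contrast and 0.08 on each enhancement versus standard. The 1/k option saves 0.09 and 0.06.

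The direction is secure for both options at any r below 1, provided some families have two or more patients and, for the exchangeable option, the working correlation is about right. The size is not secure, because family sizes, correlation and vaccination rate are all assumed. No conclusion of the trial is shown to change. This is an inexpensive improvement worth making before analysis.

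**What to change.** 1. Make all randomised family members the analysis set for the planned risk-ratio model, with family as the cluster and robust standard errors.
2. Choose one weighting and name the estimand. Weighting each member by 1/household size, with family size fixed at randomisation, keeps the household-weighted target of the index rule and removes the noise of the draw. An exchangeable working correlation is more efficient here, but its target lies between household and patient weighting.
3. Keep the one-index-patient analysis as a sensitivity analysis for meta-analysis use, with the draw made before outcomes are known.
4. Label each n as patients or families, and give both per arm.
5. Confirm that the central extraction includes end-of-campaign status for every family member.

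The cost is analysis-plan wording and one clustered model in the SAS package already named; new data collection should not be needed if item 5 is confirmed. There are two downsides. The clustered model must replace, or be combined with, the optional clinic random effects, and the plan should say which. If exchangeable weighting is chosen, the estimand shifts slightly from that of the index rule.

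### As written, patients vaccinated this season before the first text count as events in every arm; this pulls the risk ratio toward 1 and costs some power, and a common start date would avoid it cheaply.

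*Combined protocol and SAP*

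**What the plan says.** Under Statistical Analysis of Randomized Trial, the log-binomial models use "vaccination status at the end of the campaign as the outcome variable". The Objectives describe the endpoint as "receipt of influenza vaccination during the 2022-23 season". Neither gives a date from which a vaccination counts.

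On who is analysed, Selection of Patients says that any patient the health system regards as its own "will become the patient denominator". Assignment to the intervention adds: "There are no specific inclusion or exclusion criteria". All analyses are intention-to-treat, on one randomly chosen index patient per household.

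On timing, Description of the Interventions says: "Text messages will begin to be sent in early October". For patients already vaccinated this season, Assignment to the intervention says that "the patients will be dropped form the denominator of patients needing a text message reminder", and: "We will search the EHR prior to each of the text message rounds". The first round is included, so the plan allows for some patients being vaccinated before any text. The rule concerns who is texted; it does not mention the analysis set or the coding of the outcome. The same section says that the records will supply "influenza vaccination dates this upcoming season".

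**The concern.** Taken together, these statements keep a patient vaccinated before the first text in the allocated arm, and that patient is vaccinated at campaign end. The same holds in every arm. No text could have influenced these vaccinations, so they add equal numbers of events, in expectation, to each side of the comparison. The estimated ratio is then diluted relative to the effect among patients who could still respond, and the trial is less likely to detect that effect. The smallest arm (transportation, 3,050) and the callback versus bidirectional comparison (7,000 each, at 0.017) have the least power to spare.

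Adjusting for vaccination in the prior two seasons does not deal with doses already given this season.

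**Working it through.** **No figure to reproduce.** The plan contains no sample-size calculation, expected uptake, target effect or power.

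**Inputs from the documents.** Arm sizes are 232,950 (standard), 3,050 (transportation), 7,000 (callback) and 7,000 (bidirectional), which sum to 250,000. Two-sided levels are 0.017 for text enhancements and 0.05 for transportation.

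**Assumed inputs.** Share vaccinated before the first text, v: 2, 5, 10%. Later vaccination rate among the rest of the comparator arm, p0: 15, 25, 40%. True risk ratio among those patients: 1.05, 1.10, 1.15, with p1 = ratio × p0.

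**Formulas.**
- Counted as events (as written): arm risk v + (1−v)p, full n.
- Kept but coded as non-events: arm risk (1−v)p, full n.
- Excluded: arm risk p, on n(1−v).
- Power = Φ(|difference|/SE − z), unpooled SE, unadjusted.

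**Direction.** The ratio when counted is [v + (1−v)p1]/[v + (1−v)p0], which lies closer to 1 than p1/p0 for any v above zero. Relative to exclusion, the information (squared z) is multiplied by about p0/[v + (1−v)p0], which is always below 1. At p0 = 0.25 and v = 0.10 this is 0.25/0.325 = 0.77.

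**Ratio, p0 = 0.25, true ratio 1.10.** For v = 2, 5, 10%: 0.2895/0.265 = 1.092; 0.31125/0.2875 = 1.083; 0.3475/0.325 = 1.069. Pre-text vaccinations are then v/[v + (1−v)p0] = 8, 17 and 31% of control-arm vaccinations.

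**One case in full: transportation versus standard, v = 10%.**
- Counted: difference 0.3475 − 0.325 = 0.0225; SE = √(0.325×0.675/232,950 + 0.3475×0.6525/3,050) = 0.00868; z = 2.593; power = Φ(2.593 − 1.960) = 73.7%.
- Excluded: n = 209,655 and 2,745; difference 0.025; SE = 0.00857; z = 2.916; power = Φ(2.916 − 1.960) = 83.0%.

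**Power (%) at p0 = 25%, ratio 1.10: counted / kept as non-events / excluded**

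| Comparison | v = 2% | v = 5% | v = 10% |
|---|---|---|---|
| Transportation vs standard | 84.3 / 85.8 / 86.0 | 80.4 / 84.3 / 85.0 | 73.7 / 81.6 / 83.0 |
| Callback vs bidirectional | 80.3 / 82.4 / 82.7 | 75.2 / 80.6 / 81.4 | 66.7 / 77.3 / 78.9 |
| A 7,000 arm vs standard | 98.1 / 98.5 / 98.6 | 96.7 / 98.1 / 98.3 | 93.5 / 97.2 / 97.7 |

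**Whole grid** (27 input combinations × 3 comparisons = 81 cells). The loss from counting, against exclusion, has a median of 2.5 points; 57 of 81 cells lose under 5. At v = 2% every cell loses under 5. The largest losses are:
- transportation: 15.4 points (40.3 vs 55.7; ratio 1.10);
- callback vs bidirectional: 19.8 points (65.5 vs 85.3; ratio 1.15);
- a 7,000 arm vs standard: 20.6 points (57.5 vs 78.1; ratio 1.10).

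All three maxima occur at p0 = 15% and v = 10%, where 0.10/(0.10 + 0.90×0.15) = 43% of control-arm vaccinations come before the first text. The smallest loss is 0.0 for each comparison.

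**Sensitivity.** A pooled-variance formula gives levels up to 3 points higher with the same pattern (transportation, v = 10%, base case: 74.7 / 83.2 / 84.5). If the stated arm sizes are patients and households average 1.5 (assumed), the base case at v = 5% becomes 63.3 / 67.8 / 68.6 for transportation, 54.7 / 60.5 / 61.4 for callback vs bidirectional, and 85.7 / 89.5 / 90.1 for a 7,000 arm vs standard.

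**The case against.** **Season-end coverage may be the intended target.** The objective and the outcome wording both point that way, and an all-patients intention-to-treat analysis fits it. On that view nothing is attenuated; the plan simply estimates a different quantity. This largely stands, and is why the point is an improvement and not an error. The power cost of that target remains, and the plan does not discuss it.

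**Perhaps pre-text vaccinees are not in the arms at all.** Study Design says that the whole population of about 250,000 will be texted, and the arm sizes sum to that figure, so everyone randomised might be due at least one text. This is possible but not conclusive: the total is approximate, the number of texts is given only as a maximum, and no rule removes vaccinated patients before allocation.

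**The size is assumed and usually small.** This stands. For a 7,000 arm against standard, the base-case power never falls below 93.5%. The figures are also unadjusted, whereas the planned models include covariates; adjustment would change the levels but would not remove the dilution.

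**A stronger reading of the drop rule.** A reader might infer that vaccinated patients leave the analysis, so that the searches before rounds 2 and 3 would delete outcome events and breach intention-to-treat. The text does not support this: the rule is limited to patients who need a reminder, and the same word, denominator, in Selection of Patients is thin evidence for more.

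**Conclusion.** As written, pre-text vaccinations are events in all arms. For any pre-text share above zero this moves the risk ratio toward 1 and lowers power against an analysis that excludes those patients. The direction follows from algebra. The size rests wholly on assumed shares, rates and ratios: typically under 5 points of power, and 15-21 points only in the corner where about 43% of control vaccinations precede the first text.

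A reader might infer that the comparison is biased or type I error inflated. Neither follows: vaccinations before the first text are balanced across arms by randomisation. Nor do the documents show that the trial is seriously underpowered, because they give neither a power target nor the share vaccinated before early October. This is a worthwhile, inexpensive improvement, held with medium confidence as to its practical importance.

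**What to change.** 1. Set one calendar cut-off common to all arms, the campaign launch date.
2. For the primary analysis, exclude from every arm any index patient whose first 2022-23 influenza vaccination is dated before the cut-off, using the earliest date in whichever sources feed the outcome. Data Management lists CAIR2 as well as EHR data, whereas the pre-round search covers the EHR only. Count as events only first vaccinations on or after the cut-off. Using the first date settles the coding of patients with records on both sides.
3. Draw the index patient by the same rule in every arm, and state whether this is done before or after the exclusion.
4. Report season-end coverage in all randomised index patients as a sensitivity analysis.
5. State that the searches before rounds 2 and 3 only suppress messages and remove nobody from the analysis.

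Keeping early vaccinees as non-events would also restore the ratio, but on this grid it is never more powerful than exclusion, and it codes patients vaccinated this season as unvaccinated.

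**Cost.** Analysis-plan wording and a date filter; the vaccination dates are already to be obtained. The primary estimate would no longer describe total season coverage in the whole empanelled population, and the analysed n falls by the share already vaccinated. If the sponsor prefers season-end coverage as primary, saying so would settle the question but leave the power loss in place.
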